Chemotherapeutic mouthrinses and toothpastes have been shown to be efficacious in helping to remove the biofilm in conjunction with manual plaque removal with toothbrushing, flossing and oral irrigation.^{4,5} This study investigated the efficacy of an over the counter (OTC) toothpaste and mouthrinse, both produced according to the FDA's CFR21 monograph for products designed to reduce supragingival plaque and gingivitis, for reducing supragingival plaque, gingivitis, and bleeding on probing. The products used in the study were ClōSYS® Sensitive Fluoride Toothpaste, which contains 0.1% stabilized chlorine dioxide (sodium chlorite in an aqueous solution) and 0.13% w/v fluoride ion, and ClōSYS® Sensitive Rinse which contains 0.1% stabilized chlorine dioxide. Early research supports the efficacy of stabilized chlorine dioxide for reducing oral biofilm.⁶ A twice daily oral hygiene regimen using both products was tested in adult subjects diagnosed with gingivitis and early periodontitis.

Objective

The purpose of the study was to evaluate the efficacy of twice daily use of CloSYS Sensitive fluoride toothpaste and Sensitive oral rinse on gingival bleeding upon probing and supragingival plaque in patients with gingivitis or periodontitis (Stage I or II).

Study Design

This was a 90-day, self-controlled, longitudinal, non-blinded clinical trial which measured changes in clinical parameters in participants with gingivitis and Stage I or II periodontitis who applied CloSYS Sensitive fluoride toothpaste twice daily with a toothbrush and CloSYS Sensitive oral rinse twice daily after brushing. Gingivitis was defined as bleeding upon probing with no loss of attachment, and periodontitis was defined when loss of periodontal tissue support through inflammation is the primary feature.

The primary response variables were Subjects' scores on the Plaque Index (PI), Gingival Index (GI) and the number of sites with bleeding upon probing (BOP). Probing depths and clinical attachment level were assessed at baseline and 3 months. Adverse events were assessed and documented at each visit. In addition, Subjects were instructed to keep a usage diary

documenting their daily use of the toothpaste and oral rinse and any comments or observations regarding usage or adverse events.

Number of Subjects

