Subjects were given the right to withdraw from the study at any time and for any reason without prejudice to receiving future dental care at the institution. The PI documented the withdrawal/removal from the study and the reason for withdrawal/removal in the study record. If a subject experienced a complication and wanted to withdraw, if they consented, they were scheduled for an immediate follow-up/closeout examination to determine if an adverse event was present, and if so, the causation of the adverse event was recorded. Every effort was made to follow-up with subjects who withdrew on their own from the study.

Subject data only up to the time when the subjects were withdrawn was kept but was not included in the data analysis of the study.

Off Study

Subjects were considered off study when all planned study visits, early termination, and follow-up visits were completed.

Study Outcomes

This study assessed differences in clinical outcomes at baseline, 6 and 12 weeks. The primary outcomes include changes in gingival and plaque indices (GI and PI, respectively), and bleeding on probing. Because enrolled subjects presented primarily with gingivitis, changes in pocket depth and clinical attachment level were not included in the initial data analysis, as clinically, changes observed were negligible. Secondary outcomes included adverse events, compliance with the oral hygiene regimen and patient product use experience and preferences data.

14. Hypotheses

The hypotheses for the study were as follows:

- Subjects who apply CloSYS Sensitive fluoride toothpaste and Sensitive oral rinse as directed will experience reductions in PI across time.
- Subjects who apply CloSYS Sensitive fluoride Toothpaste and Sensitive oral rinse as directed will experience reductions in GI across time.
- Subjects who apply CloSYS Sensitive fluoride Toothpaste and Sensitive oral rinse as directed will experience reductions in BOP across time.

Statistical Analysis

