Data was coded and entered into an Excel spreadsheet which was then imported into IBM SPSS version 28 for analysis. Descriptive statistics were used to report demographics. The Kruskal-Wallis test, with the Dunn post-hoc test, was used to compare MGI and PI at baseline, 6 weeks and 12 weeks. Pairwise comparisons using Wilcoxon signed rank test was used to compare differences in bleeding on probing (BOP) between baseline and 12 weeks. Adverse events data, compliance data and patient product use experience data were reported using descriptive statistics. All data were de-identified and reported in aggregate form only.

REFERENCES

2. Bosshardt DD. The periodontal pocket: pathogenesis, histopathology and consequences. *Periodontol 2000*. 2018 Feb;76(1):43-50. doi: 10.1111/prd.12153. Epub 2017 Nov 30.
5. Gunsolley JC. Clinical efficacy of antimicrobial mouthrinses. *J Dent*. 2010 Jun;38 Suppl 1:S6-10. doi: 10.1016/S0300-5712(10)70004-X. Review.
8. Löe H. The Gingival Index, the Plaque Index and the Retention Index Systems. *J Periodontol*. 1967 Nov-Dec;38(6):Suppl:610-6.
9. Bessa-Rebelo M, Corrêa de Queiroz, A. Gingival Indices: State of the Art. Available at: https://www.researchgate.net/profile/Maria_Rebelo2/publication/221917002_Gingival_Indices_State_of_Art/links/544658a10cf2f14fb80f32ad/Gingival-Indices-State-of-Art.pdf Accessed January 15, 2020.

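### PI and MGI have no deciding contrast, so a fall at Day 45 that is gone by Day 90 could be reported as a reduction across time

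*Combined protocol and SAP*

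**What the plan says.** The Hypotheses section predicts a fall and names no visit: subjects using the products "as directed will experience reductions in PI across time", and likewise "as directed will experience reductions in GI across time".

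Study Outcomes sets no primary visit either: "This study assessed differences in clinical outcomes at baseline, 6 and 12 weeks", and "The primary outcomes include changes in gingival and plaque indices (GI and PI, respectively), and bleeding on probing".

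The Statistical Analysis section then gives the test: "The Kruskal-Wallis test, with the Dunn post-hoc test, was used to compare MGI and PI at baseline, 6 weeks and 12 weeks". It states no significance level, sidedness, adjustment for the Dunn pairs, deciding pair or success rule.

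BOP has one contrast, with a signed-rank test "used to compare differences in bleeding on probing (BOP) between baseline and 12 weeks". Under Study Procedures, Visit 2 (Day 45) records photographs, MGI and PI but not BOP.

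Study Design states the duration and the absence of a control group: "This was a 90-day, self-controlled, longitudinal, non-blinded clinical trial".

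**The concern.** A directional hypothesis is paired with a test that has no direction and three visits on which to reject. If PI or MGI falls by Day 45 and returns to baseline by Day 90, Kruskal-Wallis is likely to be significant. The plan contains no sentence that prevents this from being written up as a reduction across time.

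The pattern is plausible here. Every subject received a prophylaxis at Visit 1, after MGI and PI had been scored, and agreed to no further cleaning during the study. An early fall that fades could therefore occur whatever the products do. With no control group, persistence to Day 90 carries much of the inferential weight, and the plan does not require it.

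A second cost comes from the test itself. Kruskal-Wallis and Dunn treat the three visits as independent groups, although the same people are measured each time. This loses power for a fall that is sustained to Day 90.

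**Working it through.** **Inputs from the document.** 60 participants (Number of Subjects); one group measured at three visits (Study Design, Study Procedures); Kruskal-Wallis with Dunn (Statistical Analysis). The document derives no sample size or power, so there is no figure of its own to reproduce.

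**Assumed inputs.** Normal subject-level scores with SD 1 at each visit; equal within-subject correlation ρ of 0.3, 0.5 or 0.7; 5% level; Dunn either unadjusted or Bonferroni-adjusted over three pairs; all 60 subjects analysed. Results come from Monte Carlo runs of about 2,000 trials per setting, with small differences between runs.

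**Formulas.** With n = 60 per visit and N = 180 pooled scores:
- Kruskal-Wallis: H = 12/[N(N+1)] × Σ n(R̄ⱼ − (N+1)/2)², referred to chi-square on 2 df. Each term is squared, so H cannot tell a fall from a rise.
- Dunn: z = (R̄ᵢ − R̄ⱼ)/√[N(N+1)/12 × 2/n]. The denominator is √[180 × 181/12 × 2/60] = √90.5 = 9.51 and contains no ρ.
- Comparator: Wilcoxon signed-rank on the within-subject Day 0 to Day 90 differences.

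**Scenario 1: a 0.5 SD fall at Day 45, none at Day 90.**

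| Result | Share of trials, ρ = 0.3 to 0.7 |
|---|---|
| Kruskal-Wallis significant | about 80-88% |
| Friedman (paired omnibus) significant | 81-99% |
| Kruskal-Wallis significant, and Bonferroni Dunn shows a fall at Day 45 but not at Day 90 | 61-68% |
| Dunn shows a fall at Day 90, even unadjusted | about 1% or less |
| Bonferroni Dunn shows Day 90 above Day 45 | 61-67% |
| Paired Day 0 to Day 90 signed-rank, two-sided | about 5% |

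The Friedman row shows that a paired omnibus test would not close the gap. The signed-rank rate is its nominal level; if a fall is also required, it is about 2-3%.

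**Sensitivity to the size of the Day 45 fall.** The Day-45-only Dunn finding occurs in 9-16% of trials for a 0.3 SD fall and in 98-99.9% for a 0.8 SD fall.

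**Direction.** A 0.5 SD rise at Day 45 with no change at Day 90 makes Kruskal-Wallis significant in 80-88% of trials. The omnibus p-value alone cannot support a claim of reduction.

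**Scenario 2: a 0.4 SD fall at both visits, ρ = 0.5.** The SD of the within-subject change is √[2(1 − 0.5)] = 1, so its standard error is 1/√60 = 0.129. An independent-groups test works as if it were √(2/60) = 0.183, which is 1.41 times too large.

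| Route to a Day 90 reduction | Power |
|---|---|
| Paired signed-rank, 5% | about 85% |
| Dunn Day 90 pair alone, unadjusted | about 60% |
| Kruskal-Wallis significant, then unadjusted Dunn Day 90 pair | about 49% |
| Kruskal-Wallis significant, then Bonferroni Dunn Day 90 pair | about 34% |

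Of the 85 − 49 = 36 points lost, 85 − 60 = 25 come from ignoring the pairing and 60 − 49 = 11 from requiring the omnibus test first. Bonferroni would take a further 49 − 34 = 15.

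**The case against.** The strongest reply is that the plan does not stop at the omnibus test. Dunn gives the direction of each pair and includes baseline versus 12 weeks, so the plan's own output would show that the Day 90 effect is absent. This stands. It means the data are there and a careful reader would see the loss; it does not supply a rule saying which result decides.

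Three stronger readings are tempting, and the documents do not support them.
- A reader might infer that the plan accepts a significant omnibus test, or any one pair, as success. It does not say so; it is silent.
- A reader might infer from the BOP contrast that the authors chose Day 90 as the primary visit and then departed from it for PI and MGI. BOP was not measured at Day 45, so baseline versus 12 weeks was the only contrast available. It is no precedent.
- A reader might infer that the Day 45 versus Day 90 pair is wasted testing. The hypotheses speak of change across time without naming baseline, and this pair is one that exposes a lost effect.

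It is also fair to say that a question about three visits is legitimate in repeated measures. It still needs a rule for a fall that reverses. Finally, the document is written in the past tense and Study Outcomes already describes the observed attachment and pocket changes as negligible. Choosing a contrast now is a post hoc choice. That objection stands and shapes the fix.

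**Conclusion.** The concern holds as a missing decision rule together with an inefficient test for PI and MGI. It is not a finding that the plan or its authors claimed success from Day 45.

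Under the stated assumptions, a Day-45-only fall of 0.5 SD makes the planned omnibus test significant in about 80-88% of trials, against about 5% for a paired Day 90 contrast. A sustained 0.4 SD fall at correlation 0.5 is detected at Day 90 with about 85% power by the paired test, about 49% by the planned sequence without adjustment and about 34% with Bonferroni. Most of that difference is due to pairing rather than to naming the visit.

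The effect sizes, correlations, 5% level, normal scores and Dunn adjustment are all assumed, because the document gives none of them. The percentages would shift with other values. The absence of a deciding contrast does not depend on them.

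**What to change.** - Make the within-subject change from Day 0 to Day 90 the deciding contrast for PI and for MGI, because 90 days is the trial's stated duration.
- Test it with a paired test, for example Wilcoxon signed-rank, and state the level and sidedness.
- Report Day 0 to Day 45 and Day 45 versus Day 90 as secondary comparisons, also with paired methods.
- State that a reduction at 90 days is claimed for an outcome only if its Day 90 contrast shows a fall.
- Label the choice as post hoc, made after data collection, and report the planned Kruskal-Wallis and Dunn results alongside it.

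The cost is a change of wording and a re-run of existing data; no new measurements are needed. There are two downsides: a real effect confined to Day 45 becomes a secondary result, and the re-specified analysis cannot be presented as pre-specified.

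### For the three primary outcomes the plan names rank tests but no estimate of within-subject change and no confidence interval, so the size and precision of the change are left unspecified.

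*Combined protocol and SAP*

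**What the plan says.** The Statistical Analysis section of the combined protocol and SAP is the whole statistical plan. It covers the primary outcomes in two sentences. For the gingival and plaque indices: "The Kruskal-Wallis test, with the Dunn post-hoc test, was used to compare MGI and PI at baseline, 6 weeks and 12 weeks". For bleeding on probing (BOP): "Pairwise comparisons using Wilcoxon signed rank test was used to compare differences in bleeding on probing (BOP) between baseline and 12 weeks".

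Descriptive statistics are mentioned twice, each time for other data: "Descriptive statistics were used to report demographics" and "Adverse events data, compliance data and patient product use experience data were reported using descriptive statistics". The only sentence that covers every variable is "All data were de-identified and reported in aggregate form only", which names no summary measure.

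Study Outcomes states: "The primary outcomes include changes in gingival and plaque indices (GI and PI, respectively), and bleeding on probing". The section headed 14. Hypotheses predicts a direction for each outcome. For plaque, users of the products "as directed will experience reductions in PI across time"; the wording for GI and BOP is parallel. No threshold, alpha level or success rule is given.

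**The concern.** The outcomes are defined as changes, and the Objective is to evaluate efficacy, but the listed analyses only test whether a change is present. A signed rank p-value does not say by how many percentage points bleeding fell. Kruskal-Wallis with Dunn is further from the stated outcome. It compares ranks between visits as if they were separate groups, so it never works from a subject's own change.

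Three things are at stake:

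- A small fall and a large fall can both satisfy a hypothesis that asks only for a reduction, and the specified output would not tell them apart.
- The outcomes are scored on different scales in Study Procedures: percentage of sites for BOP, number of teeth scoring 2 or more for MGI, and total score divided by surfaces for PI. P-values cannot show which of them improved materially.
- The plan treats size as decisive elsewhere. Study Outcomes leaves probing depth and attachment level out of the initial analysis because their changes were judged clinically negligible. No specified output allows the same judgement for the primary outcomes.

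**Working it through.** **No figure to reproduce.** The document gives 60 subjects without a sample-size derivation. It states no alpha, power, effect size or SD.

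**What is specified for each primary outcome**

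| Outcome | Visits | Test named | Uses pairing? | Estimate of change named? | Interval named? |
|---|---|---|---|---|---|
| MGI | Days 0, 45, 90 | Kruskal-Wallis, Dunn | No | No | No |
| PI | Days 0, 45, 90 | Kruskal-Wallis, Dunn | No | No | No |
| BOP | Days 0, 90 | Wilcoxon signed rank | Yes | No | No |

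The nearest text to an estimate is the per-subject scoring in Study Procedures, including the statement that the count of affected teeth is evaluated at each visit. None of it defines a group-level change or its precision.

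**Illustration for BOP only**, since BOP alone is assigned the signed rank test.

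- From the documents: n = 60 (Number of Subjects); entry BOP above 20% of sites (Inclusion Criteria).
- Assumed: two-sided alpha 0.05; all 60 analysed; roughly normal changes; SD of change 5 to 20 percentage points.
- Known property: the signed rank test has asymptotic efficiency 3/π = 0.955 relative to the t-test under normality.

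Smallest observed change that reaches significance, in SD units:

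1.96 / √(60 × 0.955) = 1.96 / √57.3 = 0.259

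| Assumed SD of change (points) | Smallest significant fall (points) |
|---|---|
| 5 | 1.3 |
| 10 | 2.6 |
| 15 | 3.9 |
| 20 | 5.2 |

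Removal of Subjects excludes withdrawn subjects from the analysis and gives no number, so 60 is an upper bound. With 54 analysed the multiple is 0.27 SD; with 48 it is 0.29 SD. The picture does not change.

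**What an interval adds.** In simulation at an SD of 10 points (2,000 runs per setting), the signed rank test rejected in 59% of runs for a true fall of 3 points, 84% for 4 points and 100% for 15 points. The Hodges-Lehmann 95% interval had a half-width of about 2.6 points and coverage of about 95%. An observed fall of 3 points would therefore be reported as about 0.4 to 5.6 (3 ± 2.6), and a fall of 15 points as about 12.4 to 17.6 (15 ± 2.6). Both are significant; only the intervals separate them.

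**MGI and PI.** The 0.26 SD figure does not carry over. A simulation took n = 60, normal data, an equal fall at both follow-up visits and an assumed within-subject correlation of 0.3 to 0.7. At a true change of 0.37 SD of change, a signed rank test has 77 to 80% power. The Dunn comparison of baseline with 12 weeks has 22 to 67% unadjusted and 8 to 46% with Bonferroni adjustment. For these two outcomes the stated test is more likely to miss a modest change than to flag a trivial one.

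**The case against.** **Summaries may have been reported anyway.** The plan is silent on them; it does not exclude them. The sentence on aggregate reporting could cover medians or means, and the scales defined in Study Procedures are interpretable. This stands against a stronger reading: a reader might infer that the primary outcomes receive p-values and nothing else, with descriptive statistics kept for other data. The documents do not say that. What they support is that no estimate and no interval is specified. Visit medians alone would not fill the gap, because they give neither the paired change nor its precision.

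**No success rule is stated.** A reader might also infer that any significant fall would be declared efficacy. With no alpha or decision rule in the plan, that does not follow. The direction-only hypotheses leave the possibility open and do no more.

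**An interval would not show how well the products work.** This stands in full. Study Design describes a self-controlled, non-blinded trial, so there is no comparator. Every subject received a prophylaxis at Visit 1, and entry required BOP above 20%, so regression to the mean is also in play. An interval would bound a change that mixes these with any product effect. That limits what may be concluded from the estimate, but a bare p-value has the same limits and says less.

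**A responder share is not a good substitute.** The proportion at or below 20% BOP at Day 90 may look attractive. However, all subjects were selected above that level, so some would cross it by regression to the mean alone, and the plan uses 20% only for entry.

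**Conclusion.** The point holds as a gap in what the analysis specifies. For PI, MGI and BOP the plan names tests without an estimate of within-subject change or an interval, and for PI and MGI the test does not use the pairing. The changes that Study Outcomes defines as primary are therefore not quantified by the analysis as written.

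The size can be illustrated for BOP only: a fall of about 1.3 to 5.2 percentage points reaches significance. The SD range, the alpha level and full follow-up behind that figure are assumptions, not figures from the plan.

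This is a cheap and worthwhile improvement. It does not show that the tests' results are wrong, nor that summaries were withheld.

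**What to change.** In Statistical Analysis, make the main result for each primary outcome the within-subject change from Day 0:

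- BOP (percentage of sites) at Day 90, and PI and MGI at Days 45 and 90, each as the Hodges-Lehmann median paired difference with a 95% confidence interval.
- A paired test in support for all three outcomes, and the median at each visit.
- Conclusions worded from the interval and labelled as a before-after change in an uncontrolled group that also received a baseline prophylaxis, not as a product effect.

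No new data are needed. The cost is a revised paragraph and a few more output lines. The downside for the sponsor is that a small but significant change will be visible as small.
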